# F. Data Analysis Plan:

# F.1 Aim 1: Determine if insular TMS reduces cigarette craving:

F.1.1 Statistical Design: For a multivariate analysis of covariance model, we will fit a general linear multivariate model, with measures of craving before and after treatment as the outcomes. As predictors, we will fit indicator variables for treatment assignment, and FTND. We will use the Hotelling-Lawley test to assess treatment by time interaction, and the main effects of time and treatment.

F.1.2 Sample Size and Power Analysis: Li et al. conducted an experiment similar to ours, measuring craving responses to DLPFC rTMS (Cohen's d = 3.0) or sham TMS (Cohen's d = 1.9).

Based on these estimates, we will need to recruit 15 subjects to each arm (total n=30) to detect similar differences with 80% power and 0.05 significance level. Our study should achieve similar power, even with up to 25% loss to follow-up in each arm. If our loss-to-follow up is only 10% per arm, we can detect an effect size as small as 0.962 with 80% power and 0.05 significance level. Our sample size is larger or similar to other studies using similar methods.

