# I. Hypotheses and Specific Aims

The central hypothesis is that inhibitory insular TMS can be used to provide a non-invasive intervention to decrease nicotine craving, alter resting state brain connectivity, and reduce craving-associated insular activity in smokers. All experiments will be conducted in treatment-seeking smokers. These experiments are designed to evaluate the efficacy of insular neuromodulation using rTMS. Outcome measures include (1) cigarette craving measures, (2) resting-state fMRI connectivity measures, and (3) tasked-based fMRI insular activity measures. In a double-blinded two-arm (sham rTMS and inhibitory insular rTMS) randomized control trial with 20 smokers assigned to each arm, we will collect craving measurements, resting state fMRI, and task-based fMRI before and after a single session of rTMS treatment to investigate the following aims:

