# IV. Research Methods

**A. Outcome Measure(s):** Outcome measures will include (1) cigarette craving measures, (2) resting-state fMRI connectivity measures, and (3) tasked-based fMRI insular activity measures.

A.1 Neuropsychological Testing: Our primary cognitive outcome will be the change after treatment compared to before treatment in the Questionnaire of Smoking Urges – Brief Version (QSU-brief), a measures craving. An additional important question is whether craving, smoking history, smoking characteristics, or personality traits are associated with specific changes in connectivity after treatment. Thus, we will perform the following assessments prior to treatment: (1) smoking history questionnaire, (2) Fagerstrom nicotine dependence scale (FNDS), (3) Wisconsin inventory of smoking dependence motives (WISDM-68), (4) behavioral inhibitory scale and behavioral activation scale (BIS/BAS), (5) Barratt impulsiveness scale (BIS-11). The QSU-brief will be administered before and after treatment. A visual analog scale will be used to quickly assess subjects' craving during the craving visual-cue task:

The craving data before and after treatment will be used to investigate Aim #1.

A.2. Magnetic Resonance Imaging. All MRI scans will be acquired using a 3.0 T Seimens Skyra MR system using a 20-channel head-neck coil. High-resolution 3D T1-weighted scans will be acquired before treatment for image registration and normalization. T2\* weighted echo-planar imaging blood oxygen level dependent fMRI will be acquired with 3.4 x 3.4 x 3.4 mm voxels, TR 2100 ms, TE 30 ms, and flip angle 70°. Two fMRI sequences will be acquired before and after treatment: (1) a 10 minute RS-fMRI, in which subjects will be asked to lie quietly in the scanner and not think of anything in particular; and, (2) a 15 minute task-based fMRI exam during a cigarette craving cue task. fMRI data will be processed and analyzed as described in the methods section (see C.4 through C.8). Briefly, outcome measures will include insular functional connectivity (see **Aim #3**) changes at the whole brain level after treatment compared to before treatment.

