creates sound, vibrations, and electrical stimulation similar to the active coil. Subjects will undergo a brief (10 minute) neurological examination by [name] before and after rTMS treatment, which will include examination of the motor, sensory, language, abstract-thinking, memory, and spatial reasoning systems.

The specific parameters of the rTMS proposed in this study are as follows:

Parameter	Value
Manufacturer	MagnaStim
Model Name	Rapid2
510(k) or Master File Number	
Amplitude (% of motor threshold)	90%
Frequency (pulses per second) [a]	1 Hz

Train duration [b]	1500 sec (25 min)
Number of trains per session [c]	1
Number of sessions in study [d]	1
Cumulative exposure (total # of pulses = $a \times b \times c \times d$ )	1500 pulses
Intertrain interval (time between trains)	N/A

The following table is the maximum safe duration (in seconds) of a single train of rTMS, reproduced without permission from Rossi et al. Here, safety was defined as absence of seizure, spread of excitation or afterdischarge of EMG activity. Numbers preceded by > are the longest duration tested. This table was presented by consensus. The parameters proposed in our study are highlighted in yellow and well within safe limits.

Erog (Hz)	Intensity (% of motor threshold)					
Fied (EZ)	90%	100%	110%	120%	130%	
1	>1800	>1800	>1800	>360	>50	
5	>10	>10	>10	>10	>10	
10	>5	>5	>5	4.2	2.9	
20	2.05	2.05	1.6	1.0	0.55	
25	1.28	1.28	0.84	0.4	0.24	

C.4 Comparison of craving responses to treatment: QSU and visual-analogue craving measures will be compared using a multivariate analysis of covariance (see C.4.1.1). These comparisons will provide results for **Aim #1**.

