# F.2 Aim 2: Determine if insular TMS alters insular connectivity:

F.2.1 Statistical Design: A second-level random effects model will be used to compare insular connectivity by treatment and group using ANCOVA. Age will be controlled for as nuisance variables. A Monte Carlo cluster correction threshold will be applied to correct for multiple comparisons, using a voxel-wise p<0.005 and family-wise p < 0.05.

F.2.2 Sample Size and Power Analysis: Hanlon et al. measured fMRI connectivity changes after rTMS to two separate prefrontal targets, resulting in Cohen's *d* values greater than 1.9. Based on these estimates, our target recruitment goal must be greater than 6 in each arm (total n=12) to detect significant differences with 80% power and 0.05 significance level. Our sample size n=32 (after 10% attrition of fMRI data, 10% attrition of TMS administration) is similar or larger compared to other studies using similar methods. With a sample size of 32, we can detect a correlational effect size as small as 0.30 ( $f^2$ ) with 80% power and 0.05 significance level.

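### If Aim 1 models QSU-brief and the in-scanner VAS jointly, a missed cue task removes usable primary-outcome data, and the stated 0.962 belongs to a different, single-outcome test

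*Combined protocol and SAP*

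**What the plan says.** Section A.1 names the primary craving measure: "Our primary cognitive outcome will be the change after treatment compared to before treatment in the Questionnaire of Smoking Urges" (brief version). The same section adds a second measure: "A visual analog scale will be used to quickly assess subjects' craving during the craving visual-cue task". That task is a 15-minute scanner run, done once before and once after rTMS. In the C.1 timetable the post-treatment QSU-brief is a separate 2-minute form, completed after the second MRI.

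C.4 says "QSU and visual-analogue craving measures will be compared using a multivariate analysis of covariance". F.1.1 says "we will fit a general linear multivariate model, with measures of craving before and after treatment as the outcomes", with treatment and FTND as predictors and a Hotelling-Lawley test of treatment by time and of the main effects. F.1.1 does not say whether the two instruments share one model, and it gives no rule for missing outcomes.

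On numbers, Section I describes a "randomized control trial with 20 smokers assigned to each arm". F.1.2 requires 15 per arm, says that similar power survives up to 25% loss per arm, and adds: "If our loss-to-follow up is only 10% per arm, we can detect an effect size as small as 0.962 with 80% power". For the imaging aims, F.2.2 counts losses differently: "Our sample size n=32 (after 10% attrition of fMRI data, 10% attrition of TMS administration"); F.3.2 uses the same figure.

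**The concern.** A classical multivariate linear model with a Hotelling-Lawley test is fitted to participants who have all outcomes. If pre and post QSU-brief and pre and post VAS are the four outcomes, completing both scanner cue tasks becomes a condition for entering the craving analysis. The QSU-brief itself does not need the scanner. Section D lists claustrophobia, fatigue and frustration with the cue task as common and lets participants stop at any time, so some undone tasks are to be expected.

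Two things are at stake. Usable readings of the primary craving outcome could be discarded. And F.1.2 would attach a detectable effect to an analysis that it does not describe, because a two-instrument test spends a second degree of freedom and its power depends on how the VAS behaves.

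**Working it through.** **Inputs from the documents.** 20 per arm; 10% loss in F.1.2, so 20 × 0.90 = 18 per arm (derived, not printed); 25% loss, so 20 × 0.75 = 15 per arm; F.2.2 attrition, 40 × 0.9 × 0.9 = 32.4, stated as 32, or 16 per arm; one covariate (FTND); alpha 0.05; power 80%. F.1.2 cites within-arm effects of 3.0 and 1.9. The difference of 1.1 is inferred.

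**Assumptions.** Two-sided test, no variance reduction from FTND, effects in SD units of the change score.

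**Reproducing F.1.2.** For one outcome and one covariate, the treatment-by-time test is F with 1 and 2n − 3 degrees of freedom and noncentrality n·d²/2. At n = 18 the critical value is 4.139. With d = 0.9622 the noncentrality is 18 × 0.9622²/2 = 8.33 and power is 80%. So 0.962 is the single-outcome figure (0.961 without the covariate). For d = 1.1 a two-sample t-test needs n = 14.002, rounded up to the stated 15 per arm.

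**How many could be lost.** Only an undone or aborted cue task loses the VAS. The one fMRI exclusion rule given (C.5) is head movement above 2 mm, and a scan rejected for motion can still have ratings. F.2.2 does not split its 10% by cause. The joint analysis therefore has between 18 and 18 × 0.9 = 16.2, about 16, per arm. At 16 the single-outcome detectable effect is 1.02.

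**Joint test of two change scores.** F with 2 and 2n − 4 degrees of freedom and noncentrality n·D²/2, where D is the multivariate distance between arms. If the VAS adds nothing beyond QSU-brief, D = d. If both instruments move by d and their changes correlate r, D² = 2d²/(1 + r). For d = 0.962:
- r = 0.5: D = 0.962 × √(2/1.5) = 1.111
- r = 0.7: D = 0.962 × √(2/1.7) = 1.043

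Power at a QSU-brief effect of 0.962:

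| Per arm | QSU-brief alone | Joint, VAS adds nothing | Joint, equal effect, r = 0.7 | Joint, equal effect, r = 0.5 |
|---|---|---|---|---|
| 18 | 80% | 69% | 77% | 82% |
| 16 | 75% | 63% | 71% | 76% |

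**The 25% allowance.** At d = 1.1 and 15 per arm the single-outcome noncentrality is 15 × 1.21/2 = 9.075, and power is 83%. With the same noncentrality, the joint test with an uninformative VAS has 72%. At 16 per arm the two figures are 85% and 75%.

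**The case against.** The strongest reply is that the joint model is an inference. Pre and post values of one instrument already make F.1.1 multivariate, and C.4 could mean one model per instrument. This stands as a caveat. Against it, C.4 names both measures with a single analysis. With one instrument, the treatment-by-time contrast has one dimension and Hotelling-Lawley reduces to an ordinary F test. The joint reading is the more natural one, but the text does not settle it.

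Three stronger readings are tempting and are not supported.

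- **That Aim 1 will fall to 16 per arm.** Loss of fMRI data is not loss of VAS ratings, so 16 is the worst case on F.2.2's figures.
- **That F.1.2 makes no allowance for loss.** Its 25% case reaches 15 per arm, and a single-outcome test keeps 83% power there at 1.1. The 0.962 sentence is explicitly conditional on 10% loss and is correct for one outcome.
- **That a joint test must be weaker, or that the comparison is biased by dropout.** With equal effects and r = 0.5, the joint test at 18 per arm has 82% power, slightly above QSU-brief alone. As for bias, the documents put headache or scalp discomfort at about 10% but call it self-limited. They tie it neither to withdrawal nor to one arm, and they describe a sham coil with similar sensations. Any bias figure would rest on outside assumptions. If leaving depended on unseen post-treatment craving, a mixed model would not remove the bias.

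**Conclusion.** The concern holds in a conditional form. Under the natural joint reading, participants with complete QSU-brief data but a missing cue task drop out of the analysis of the primary craving outcome. The number is between none and about two per arm (18 down to 16).

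The 0.962 is sound for a QSU-brief-only test at 18 per arm. It is not a property of a joint test, whose power at that effect runs from 69% to 82% at 18 per arm and from 63% to 76% at 16 over the cases considered. The 25% allowance protects the head count for a single outcome, but not a joint test with an uninformative VAS (72% at 1.1 with 15 per arm). The VAS effect and the correlation are assumptions, since the documents give neither.

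**What to change.** In F.1.1, test the QSU-brief treatment-by-time effect in its own model, with FTND as covariate, on all randomised participants with QSU-brief data. State that a missing VAS removes nobody from it. Analyse the VAS separately as a secondary craving measure, and align C.4 with this.

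In F.1.2, state that 0.962 applies to the QSU-brief-only test at 18 per arm. If a joint test is kept, report its power with the assumed VAS effect and correlation. Do not print a multivariate distance beside 0.962, because the two are on different scales.

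The cost is plan wording and a different model call, with no extra participants or visits. The one thing given up is the VAS's contribution to the primary test, which could have added a little power if it moved with QSU-brief and correlated only moderately.

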C.2 Demographic. Psychological, Smoking, and Craving Assessments: Subjects will complete a basic demographic survey to document the date of birth, sex, ethnicity, education, handedness, and use of glasses. Age and sex must be determined because gray matter characteristics and brain function vary by age. Education and handedness must be documented because brain function is affected by these variables. The use of glasses must be documented because if subjects are unable to see the images during the craving cue task, it can introduce a bias in the data.

Medical history, current medications, and surgical/procedural history will be documented. [name] will review this information to ensure that the subject meets no exclusion criteria, and to ensure that the subject is taking no medications that lower the seizure threshold.

Subjects will complete a brief smoking history questionnaire. This will characterize the severity and nature of the subject's cigarette dependence, which may affect their responses to craving cues.

Subjects will complete the Fagerstrom Nicotine Dependence Scale (FNDS). This is a valid and reliable standardized survey to quantify the degree of cigarette dependence.

Subjects will complete the Wisconsin Inventory of Smoking Dependence Motives (WISDM-68). This is a valid and reliable 68-item standardized survey designed to characterize the psychological constructs that motive an individual subject's smoking behaviors.

Subjects will complete the Questionnaire on Smoking Urges – Brief (QSU-Brief). This is a valid and reliable standardized survey to quantify a subject's current intensity of craving. This is the only standardized survey that in addition to being administered prior to rTMS treatment will also be administered after rTMS treatment.

Subjects will complete the Behavioral Inhibition Scale and Behavioral Activation Scale (BIS/BAS). The Behavioral Inhibition and Activation Scale is a 20-item self-reported questionnaire

used to measure responsiveness of motivational systems. The first component is the Behavioral Inhibition Scale, which is used to quantify avoidance behaviors and reactions to the anticipation of punishment. The second component is the Behavioral Activation Scale, which is used to quantify positive affective and approach response tendencies to appetitive stimuli.

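### The Aim 1 analysis does not adjust for the baseline QSU-brief score the trial already collects; the planned test is valid, but baseline-adjusted ANCOVA would usually be more powerful for one degree of freedom

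*Combined protocol and SAP*

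**What the plan says.** Section A.1 defines the craving outcome as a change: "Our primary cognitive outcome will be the change after treatment compared to before treatment in the Questionnaire of Smoking Urges". It also says that "The QSU-brief will be administered before and after treatment". Section C.2 (assessments) confirms this, saying of QSU-brief: "This is the only standardized survey that in addition to being administered prior to rTMS treatment will also be administered after rTMS treatment".

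Section F.1.1 describes a general linear multivariate model "with measures of craving before and after treatment as the outcomes". The right-hand side of the model is short: "As predictors, we will fit indicator variables for treatment assignment, and FTND". The tests are listed together: "We will use the Hotelling-Lawley test to assess treatment by time interaction, and the main effects of time and treatment". Section C.4 sends both QSU and the visual analogue craving measure to this multivariate analysis of covariance.

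Section F.1.2 sizes the trial from a cited DLPFC study with d = 3.0 (active) and 1.9 (sham), giving 15 per arm. It adds "Our study should achieve similar power, even with up to 25% loss to follow-up in each arm" and says that with 10% loss per arm "we can detect an effect size as small as 0.962 with 80% power and 0.05 significance level".

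**The concern.** Baseline craving enters F.1.1 only as an outcome. Although the analysis is called an analysis of covariance, FTND is the only covariate named. For one measure taken at two times, the treatment-by-time test reduces to comparing mean change between arms, adjusted for FTND.

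The change score subtracts the whole baseline value, whatever the correlation between the two measurements. ANCOVA subtracts only the part that predicts the post-treatment score, which removes the noise from chance baseline imbalance. That imbalance is random and does not bias the planned test. What is at stake is precision, in a trial of 20 per arm that expects to analyse 15 to 18 per arm.

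There is also a smaller wording gap. F.1.1 lists the interaction and both main effects without saying which one decides Aim 1. The main effect of time does not compare the arms, and the main effect of treatment averages in the pre-treatment score. H1 (a comparison with sham) and section A.1 (change) point to the interaction, but F.1.1 does not say so.

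**Working it through.** **Inputs from the documents.** 20 per arm randomised (section I); d = 3.0 and 1.9, 80% power, significance level 0.05, losses of 25% and 10%, detectable effect 0.962 (F.1.2).

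**Assumptions.** Two-sided testing, which reproduces the plan's figures. Effect sizes in units of the SD of change. The pre-post correlation ρ and the SD ratio k = baseline SD / post-treatment SD are not in the documents and are varied. All figures are for QSU-brief tested alone.

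**The plan's own figures.**
- Difference in d: 3.0 − 1.9 = 1.1. A two-sample t-test (noncentral t) gives 82.8% power at 15 per arm and just under 80% at 14, so 15 per arm reproduces.
- 20 × 0.75 = 15 and 20 × 0.90 = 18 per arm.
- The effect detectable with 80% power at 18 per arm is 0.961, against the stated 0.962.

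**Variances, with post-treatment SD = 1.**
- Change score: 1 + k² − 2ρk.
- Baseline-adjusted ANCOVA: 1 − ρ².
- Difference: (k − ρ)², which is never negative.

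For example, with k = 1 and ρ = 0.5, the change variance is 1 + 1 − 1 = 1 and the ANCOVA variance is 1 − 0.25 = 0.75. An effect of 0.962 SDs of change becomes 0.962 / √0.75 = 1.111 residual SDs. Against this, ANCOVA uses one residual degree of freedom and pays for chance imbalance of the covariate between arms. Power is therefore averaged over that imbalance, with R² distributed as Beta(q/2, (N − 1 − q)/2) for q covariates and N participants.

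**Power (%).** The change-score column does not depend on ρ or k.

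| Setting | Change | ANCOVA ρ=0.3 | 0.5 | 0.7 | 0.8 | 0.9 |
|---|---|---|---|---|---|---|
| 18/arm, d=0.962, k=1, no FTND | 80.1 | 92.8 | 89.0 | 84.9 | 82.8 | 80.8 |
| Same, FTND in both models | 78.8 | 91.9 | 87.9 | 83.7 | 81.6 | 79.5 |
| 18/arm, d=0.962, k=0.8, no FTND | 80.1 | 87.6 | 83.1 | 79.6 | 78.8 | 80.8 |
| 18/arm, d=0.962, k=1.25, no FTND | 80.1 | 97.3 | 95.4 | 93.6 | 93.1 | 94.2 |
| 18/arm, d=1.1, k=1, no FTND | 89.4 | 97.4 | 95.3 | 92.8 | 91.4 | 89.9 |
| 15/arm, d=1.1, k=1, no FTND | 82.8 | 94.2 | 90.8 | 87.1 | 85.2 | 83.3 |
| 15/arm, d=0.962, k=1, no FTND | 72.0 | 87.1 | 82.1 | 77.2 | 74.8 | 72.5 |

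The last row combines the 25% loss with the effect that F.1.2 quotes only for 10% loss. The plan makes no power claim for that combination.

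**Detectable effect** (80% power, 18 per arm, k = 1, SDs of change): from 0.96 to 0.79, 0.85, 0.90, 0.93 and 0.95 at the same five correlations.

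**Where the gain ends.** With k = 1, the two methods break even at ρ of about 0.94. With k = 0.8, ANCOVA is slightly worse for ρ of about 0.67 to 0.88. The largest loss at d = 0.962 occurs at ρ = k: 1.3 points at 18 per arm and 1.7 points at 15 per arm.

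**Simulation check** (40,000 trials per setting, 18 per arm, d = 0.962, FTND in both models and not prognostic). The change score gave 78–79%. With k = 1, ANCOVA gave 91.9, 88.0, 83.6, 81.3 and 79.6%. Type I error was 4.8–5.1% for both methods.

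**The case against.** The strongest reply is that nothing here is an error. The planned test is valid, matches the outcome as defined, and at the plan's own d = 1.1 has 83% power at 15 per arm and 89% at 18, both above target. That stands, and it is why the point is minor.

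The second reply is that the size of the gain is assumed. Neither ρ nor k is given; with k = 0.8 and ρ between 0.7 and 0.9 there is no useful gain. The standardiser matters too, because F.1.2 does not say which SD its d values use. If 0.962 were in raw-score SDs (k = 1, 18 per arm, no FTND), change-score against ANCOVA power would be 66 against 82% at ρ = 0.3, 80 against 89% at 0.5, 95 against 97% at 0.7, and 99.3 against 99.6% at 0.8. This makes the size uncertain in both directions. ANCOVA still leads at each of those correlations, and its worst loss remains small.

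The third reply is that section C.4 can be read as one joint model of QSU and the visual analogue scale. If so, the figures above do not describe that joint test, and replacing it with separate ANCOVAs raises a multiplicity question about the second measure. This also stands. It limits the figures to QSU-brief, which section A.1 names as the primary measure, and it means the role of the visual analogue scale has to be stated. It does not change the fact that baseline craving is not used as a covariate.

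**Conclusion.** The point holds as a minor efficiency improvement. F.1.1 leaves unused a covariate that the trial already collects. The planned interaction test controls type I error, and the stated sample size reproduces.

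At 18 per arm, d = 0.962 and equal SDs, baseline adjustment adds about 13 points of power at ρ = 0.3, 9 at 0.5, 5 at 0.7 and under 1 at 0.9. The worst loss is 1.3 points (1.7 at 15 per arm). These sizes rest on assumed ρ and k, on effects measured in SDs of change, and on QSU-brief being tested alone. The direction is more secure than the size: gains can be large, and losses are confined to ρ close to k. The unclear status of the main effects is a wording gap only.

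**What to change.** Add to F.1.1, before any unblinded analysis:

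> The between-arm comparison of QSU-brief will be made by ANCOVA of the post-treatment score with treatment arm, baseline QSU-brief and FTND as predictors. Its treatment coefficient (two-sided 0.05) is the test for the primary QSU-brief outcome. The main effects of time and treatment in the multivariate model are descriptive. Visual analogue craving will be analysed in the same way with its own baseline.

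The sponsor should also state where the visual analogue measure stands relative to QSU-brief, given the joint wording of C.4 and the cue-craving wording of H1. If both are to support confirmatory claims, multiplicity needs a rule.

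If the multivariate model is kept, one sentence is enough: the QSU-brief treatment-by-time interaction is the test for the primary QSU-brief outcome. That closes the wording gap but forgoes the power gain.

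The cost is analysis-plan text only, with no new data, visits or participants. The ANCOVA uses one residual degree of freedom (33 to 32 at 18 per arm with FTND in the model) and carries the small possible loss of power given above.
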